### **Aims, purpose, or objectives:**

1. To study the feasibility of HCP using a wearable brain sensing wellness device (Muse-S™) during a time of increased workload, patient volume and stressors.
2. To assess the association between duration of active state and calm state as measured by the wearable brain sensing wellness device (Muse-S™), and quality of life (QOL), subjective stress, sleep and resilience.

The primary outcome will be the adherence to the Muse-S™ by summarizing the frequency of use and duration of use each time it was accessed.

The secondary outcomes will include:

- change in stress score over time
- measures of QOL, resilience and coping score in HCP at specific time points post baseline.

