**Study Design and Methods**

**Methods:**

All study participants will receive the Muse S™ Headband system at study entry and will be asked to utilize it at least 4 times per week for a minimum of 10 minutes each time over a period of 3 months (12 weeks). They will be followed for a period of 6 months (3 months of treatment and 3 months post treatment) according to the schedule below.

We will assess the following:

- Type of meditation the patient has selected from the 3 available options: Mind Meditation, Guided Meditation and Go-to-sleep meditation.
- Frequency and duration of use from baseline to month 3 (end of treatment). The participants will be informed at baseline that for best results, it will be recommended that they use it a minimum of 10 minutes, at least 4 times per week for over 3 months. If they are short on time, they can break up the 10 minutes and do shorter meditations.

- Changes in QOL, stress, resilience, and sleep score from baseline through week 2, month 1, month 3 and month 6.

Visit No.	Consent /screen /baseline	Treatment Phase			Follow up Phase
	1	2	3	4	5
Visit Type	face to face	Phone/ email	Phone/ email	face to face/phone/ email	face to face/phone/ email
Visit Days	0	14	30	90	180
Informed Consent	X				
Inclusion/Exclusion	X				
Demographic and History Form	X				
Depression	X	X	X	X	X
Burnout	X			X	X
Resilience	X	X	X	X	X
Sleep	X	X	X	X	X
Quality of Life	X	X	X	X	X
Stress Scale	X	X	X	X	X
Satisfaction Survey					X
Adverse Events 		X	X	X	X
CBS Cognitive Tests	X			X	X
Concomitant Medication 	X	X	X	X	X
Instructions for Muse-S™	X				
End of Treatment/End of Study Forms				X	X

1 = For visit 5, only serious adverse events will be newly collected; 2 = For visit 5, only newly added concomitant medications will be collected

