#### Consent and Screen:

Study coordinator will meet with the potential participant who has expressed an interest in participating in the study. The study coordinator will begin by introducing the study details, and after determining that the subject has continued interest in study participation, will move on to the study consent. If the subject

chooses to consent, the study coordinator will screen the participant for study entry inclusion/exclusion criteria. If the study entry criteria are met, the subject will begin their study participation. They will be asked to complete the study surveys/questionnaires.

*Please note:* Participants must have access to an iOS or Android capable device to take part in this study in order to interact with the Muse-S™ Headband system.

Treatment phase:

During the first three months of study, participants will be asked to complete the online study intervention using the Muse-S™ headband. Participants will be contacted via telephone and online (REDCap) for study visits at day 14 and 30. At day 90, they will be asked to return to the clinic for an in-person visit (telephone and online will be alternatives).

Study Follow-Up Visits:

The study will consist of a 6-month visit post baseline (3-month post end of intervention). Participants will be asked to complete an in-person visit, if possible (telephone and online will be the alternative).

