General Study Information

Principal Investigator: [name]

A Study Title: A Feasibility study evaluating Mindfulness-Based Intervention Assessing A Wearable Wellness Brain Sensing Device (Muse-S™) in Practicing Health Care Providers.

Protocol date: 23 Sept 2024

Data Analysis

Data Analysis Plan:

Demographic characteristics are described using mean and standard deviations or frequencies and percentages based on the type of variable. For the primary aim of assessing feasibility, descriptive statistics and graphical displays will be presented for data obtained on frequency and duration of use over the 12 weeks of treatment. A linear mixed model with repeated measures for each time point that stress and sleep were taken will be utilized to estimate the association between the average of time spent using the Muse-S™ with the stress and sleep level outcome. Age, sex, and the total amount of meditation time at each interval will also be adjusted for in the model. As secondary outcomes, the results of the LASA, resilience, coping, and cognitive testing will be analyzed using linear mixed models with repeated measures to determine changes over time. In all cases, results will be summarized using point-estimates and corresponding 95% confidence intervals. Given the number of outcomes assessed, all analyses will be considered exploratory.

Endpoints:

Primary Hypothesis:

- a) HCP enrolled in this study will find the Muse-S™ Headband system easy to use and will use it often during the work week.

Secondary Hypotheses:

- a) Stress score will be lower and sleep score will be improved when compared to the baseline measures for those who use the Muse-S™ system as directed.
- b) As the use of the Muse-S™ system increases, QOL, resilience and coping will improve.

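### The stress and sleep model names no visit effect but adjusts for raw meditation totals over unequal intervals, so the interval-total coefficient can absorb much of any drift shared by all participants

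*SAP*

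**What the plan says.** The SAP (Data Analysis Plan) specifies, for stress and sleep, "A linear mixed model with repeated measures for each time point that stress and sleep were taken". Its purpose is "to estimate the association between the average of time spent using the Muse-S™ with the stress and sleep level outcome". It then adds: "Age, sex, and the total amount of meditation time at each interval will also be adjusted for in the model". No visit or time effect is named, the totals are not scaled to the length of the interval, and nothing says how the baseline or Day 180 records enter.

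The SAP's next analysis sentence, on quality of life, resilience, coping and cognition, does give change over time as the purpose: those outcomes "will be analyzed using linear mixed models with repeated measures to determine changes over time". Stress and sleep get no such statement. Yet the Protocol (Aims) lists "change in stress score over time" as a secondary outcome, and the SAP's secondary hypothesis (a) is that "Stress score will be lower and sleep score will be improved when compared to the baseline measures".

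The Protocol (Study Design and Methods) sets the assessments: "Changes in QOL, stress, resilience, and sleep score from baseline through week 2, month 1, month 3 and month 6". The visit table there gives Days 0, 14, 30, 90 and 180.

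**The concern.** Every participant receives the device, so nothing inside the study separates the passage of time from the effect of use. Stress may change for everyone for reasons unrelated to use: adaptation, easing of the pandemic, or repeated completion of the same forms. A visit effect would take up that shared change. Without one, the model puts it on whichever listed covariate moves with time, and the only listed covariate that must do so is the interval total, because the intervals lengthen.

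The output could then show minutes meditated going with lower stress when use has no effect. This is the only analysis the SAP describes for stress and sleep, and it serves the Protocol's second aim.

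**Working it through.** The documents give no power or sample-size figure for this model, so there is nothing to reproduce first.

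**1. Totals against time.** Inputs: visit days 0, 14, 30, 90 and 180 (Protocol visit table), and requested use of at least 4 × 10 = 40 minutes per week (Protocol, Methods). Total = 40 × days ÷ 7.

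| Interval | Days | Total at 40 min/week |
|---|---|---|
| 0–14 | 14 | 80 |
| 14–30 | 16 | 91 |
| 30–90 | 60 | 343 |
| 90–180 | 90 | 514 if use continues, 0 if it stops |

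Correlation of the total with study day, with Day 0 given a total of 0:
- Days 0–90: sum of cross-products 17,491; sums of squares 4,707 (days) and 66,189 (totals). So r = 17,491 ÷ √(4,707 × 66,189) = 0.99.
- Days 0–180, use continued: r = 0.98.
- Days 0–180, no use after Day 90: r = 0.06.

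The third case is open because the Protocol assesses use only from baseline to Month 3, although participants keep the headband (Subject Retention).

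**2. Simulation with no true use effect.** n = 40 (Protocol, Target accrual), random-intercept model fitted by REML, no dropout. Neither assumption set below comes from the documents.
- Set A: PSS between-person SD 4.6 and within-person SD 3.8; mean use 40 min/week, log-SD 0.6.
- Set B: PSS SD 6 and within-person correlation 0.6; log-normal use around 40 min/week, log-SD 0.5 between and 0.3 within persons.

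The variances are practically the same: √(4.6² + 3.8²) = 5.97 and 4.6² ÷ 35.6 = 0.59. Agreement between the sets therefore does not test the SD assumption.

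Set B, no visit term, linear fall to Day 90 and flat afterwards (600 runs per scenario). Entries are rejections of the interval-total coefficient at 5%:

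| Records used | Fall of 2 | Fall of 4 |
|---|---|---|
| Days 14–90 | 43% | 92% |
| Days 0–90 | 54% | 98% |
| Days 0–180, no use after Day 90 | 25% | 68% |
| Days 0–180, use continued | 71% | 99.8% |

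Set A, falls of 1/2/3 points by Day 90 (800 replicates for Days 0–90; for Day 180, 400 replicates with a within-person log-SD of 0.2 added):
- Days 0–90: 17%/48%/83% with linear drift; 11%/25%/47% with a single drop after Day 0.
- Day 180 at zero use, drift ending at Day 90: 11%/21%/43%; single drop: 10%/16%/25%.
- Day 180 at zero use, drift continuing to Day 180: 6%/4%/4%.
- Day 180 at 30% of earlier use, drift continuing: 25%/62%/92%.

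With zero drift, Set B rejects in 4–8% of runs for all coefficients.

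**3. How much drift is absorbed.** Set B, fall of 4 points:
- Days 0–90: coefficient −0.834 per 100 minutes; −0.834 × 3.43 = −2.86, about 70% of the fall.
- Days 0–180, no later use: −0.465 × 3.43 = −1.59, about 40%.

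**4. The average-use coefficient.** Taken as one value per person (Set B, fall of 4), it moves by +0.13 to +0.36 PSS points per 10 min/week, towards more stress, with 8–15% rejections. If the average is taken per interval, which the SAP's wording allows, the shift is +0.03 to +0.38 with 7–62% rejections.

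**5. With categorical visit added (Set B).** The interval total is rejected in 4–6% of runs in all 12 scenarios, with a mean coefficient within about 0.02 per 100 minutes of zero.

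**6. Visit windows.** The Protocol (Study Visit Windows) runs each window from midpoint to midpoint, so the Day 14 visit may fall on Days 7 to 22. At an identical 40 min/week its total could be 40 × 7 ÷ 7 = 40 to 40 × 22 ÷ 7 = 126 minutes.

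**The case against.** - **A visit factor may be intended.** The repeated-measures wording could imply one, and the covariate sentence adds to a model already described, so its list need not be complete. The sentence on the other outcomes names no time term either, yet needs one. This stands: a reader might infer that the SAP excludes visit, but the text shows only that visit is not specified. The same wording can equally describe the covariance structure alone.
- **Not all drift is absorbed.** A reader might infer that any common drift is credited to meditation. It is not. Absorption is partial, weaker when Day 180 enters with zero use, and in one plausible case the error rate is nominal.
- **The inflation falls on an adjuster.** The stated exposure is average use, whose coefficient moves the other way and, as a per-person average, only modestly. A reader might infer that the stated exposure would show a false benefit; the documents do not support that. But the SAP does not say which use coefficient will be interpreted, and both are measured in minutes of meditation.
- **Totals are a defensible measure.** The Protocol's hypothesis is framed in terms of amount of use, and once visit is included raw totals give about 5%. Rescaling is therefore not needed to remove the bias. A simulated power gain for minutes per week (50% against 78%) was built in by generating the effect on that scale and should not be claimed.
- **The study is exploratory.** This limits the consequence. It does not correct a biased coefficient, and the SAP promises estimates with 95% intervals throughout.

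**Conclusion.** The point holds as a gap in specification. If the model is fitted with only the terms the SAP lists, a shared linear fall of 2 to 3 PSS points by Day 90 makes the interval total falsely significant in roughly 50–85% of trials on Days 0–90, and in 20–45% if Day 180 enters with zero use. The rate ranges from near nominal (drift continuing to Day 180, no use after Day 90) to higher still (use continuing).

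The link between totals and time follows from the Protocol's schedule at constant use. The percentages rest on the assumed SDs, use distributions and drift shapes; a larger SD with the same fall would lower them. Only PSS was simulated. The mechanism is the same for sleep, but its size there is not quantified.

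The listed terms also do not estimate the change from baseline that secondary hypothesis (a) concerns. The descriptive primary aim is unaffected, so this should be settled before analysis but does not threaten the study's main result.

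**What to change.** In the SAP's stress and sleep models:

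1. State visit as a categorical fixed effect. This brings the interval-total error rate back to about 5% and supplies the change from baseline for secondary hypothesis (a). Report that change at a stated level of use, since with use in the model the bare visit coefficient refers to zero use in the interval. In a single-group study it describes change and does not isolate the effect of the device.
2. State how Day 0 enters (for example, as an outcome record with use set to zero). State whether Day 180 enters the use model and, if so, what use is assigned to Days 90–180.
3. Secondary: express interval use as minutes per week, that is logged minutes ÷ actual days since the previous visit × 7, because the visit windows are wide. Keep one use measure, or two that do not duplicate each other, and say which is interpreted.

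The cost is SAP wording plus three degrees of freedom for visit, or four with Day 180. Session times and durations are already available from the device server (Protocol, Server Data).

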## Research Question and Aims

**Hypothesis:** Healthcare providers (HCP) often deal with patients who are experiencing a variety of ailments, symptoms, and infections at the time of the face-to-face visit. There is an inherent stress that exists when one realizes the life of another being rests in their hands and capabilities. In addition, whereas the risk of contracting diseases in the course of caring for others has always existed, it has never been more evident than during this time of the Covid19 pandemic. The stress of caring for others while worrying about the potential ramifications of their care management decisions and the possibility of contracting Covid19 and inadvertently passing said disease to others (friend and family included) has significant physical and mental health ramifications for HCP. Whereas it has been touted that mindfulness can be a benefit to physicians in the front line, little guidance exists as to how this can be learned and practiced by HCP during such a busy time with little respite. We postulate that using a novel biofeedback-assisted meditation device (Muse-S™) often during the workday can provide mindfulness training to increase calm state brain activity in physicians during a busy practice in the midst of a pandemic. We hypothesize that the greater amount of time the HCP uses this tool, the greater amount of resilience s/he builds, providing needed mental support.

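### SAP hypothesis (b) links QOL and resilience to Muse-S use, but LASA and resilience are modelled only for change over time; Aim 2's calm- and active-state durations enter no model, and no instrument is identified for coping

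*SAP*

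**What the plan says.** **Hypotheses and aims.** Secondary hypothesis (b) in the SAP (Endpoints) reads "As the use of the Muse-S™ system increases, QOL, resilience and coping will improve". The protocol (Research Question and Aims) expects that "the greater amount of time the HCP uses this tool, the greater amount of resilience s/he builds". Aim 2 (Protocol, Aims, purpose, or objectives) is "To assess the association between duration of active state and calm state as measured by the wearable brain sensing wellness device", related to QOL, stress, sleep and resilience. Secondary hypothesis (a) predicts lower stress and better sleep "when compared to the baseline measures for those who use the Muse-S™ system as directed".

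**Models.** The SAP's Data Analysis Plan has two kinds of mixed model. For stress and sleep, the purpose is "to estimate the association between the average of time spent using the Muse-S™ with the stress and sleep level outcome", and "the total amount of meditation time at each interval will also be adjusted for in the model", together with age and sex. For the other outcomes, "LASA, resilience, coping, and cognitive testing will be analyzed using linear mixed models with repeated measures to determine changes over time".

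**Outcomes.** The protocol lists change in stress over time, and QOL, resilience and coping scores at set times after baseline, as secondary outcomes. Study Design and Methods lists changes from baseline in QOL, stress, resilience and sleep. The SAP calls all analyses exploratory and promises point estimates with 95% confidence intervals.

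**The concern.** The models and the hypotheses appear to be crossed. Hypothesis (a) is about change from baseline, but its outcomes (stress, sleep) get a use-association model. Hypothesis (b) is about use, but its outcomes (QOL, resilience) get a change-over-time model. Aim 2 names an exposure that no model contains.

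An analyst who follows the SAP exactly would therefore have nothing to report on whether more use goes with more resilience, or on calm- and active-state time. An analyst who fills the gap later would choose the use metric, the brain-state variable and the cut-off for the as-directed group after seeing the data. Confidence intervals and an exploratory label do not protect against that kind of selection.

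**Working it through.** The documents state no power, effect size or SD, so there is no plan figure to reproduce. The main check is a line-by-line match.

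**1. Hypothesis (b) against the models.** It names QOL, resilience and coping. QOL (LASA) and resilience (CD-RS10) have instruments; both are modelled for change over time. Outcomes with a use term: 0 of 2.

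**2. Can a change-over-time model answer it indirectly?** A simulation on assumed inputs says no: 40 participants, baseline and one follow-up, mean change 0.4, between-person SD 1, residual SD 0.7, standardised use, 200 samples per row.

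| True use slope | Time effect, time-only model | Use slope, time × use model |
|---|---|---|
| 0 | 0.41 | 0.00 |
| +0.4 | 0.40 | 0.42 |
| −0.4 | 0.40 | −0.39 |

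The time effect is nearly the same whether heavier users gain more, the same or less.

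**3. Aim 2.** Exposures: active-state and calm-state duration. In a SAP model: 0 of 2. Of its four outcomes, stress and sleep have use time as a stand-in (2 of 4); QOL and resilience have neither.

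**4. Coping.** The protocol's assessments cover depression, burnout, QOL, stress, resilience, sleep, cognition and satisfaction. None is described as measuring coping, and the five-visit schedule has no coping row.

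**5. The as-directed group in hypothesis (a).** The SAP does not define it. Study Design and Methods asks for at least four uses a week of ten minutes or more over 12 weeks: 4 × 12 = 48 sessions, 48 × 10 = 480 minutes. It also allows the ten minutes to be split. The Intervention text describes the requirement as daily: 7 × 12 = 84 sessions, or 840 minutes at ten minutes each. The ratio is 84/48 = 1.75. The two passages must be reconciled before the group can be defined.

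**6. Baseline contrasts when use is in the model.** Write score = a + b(visit) + g × use. Then b is the change at zero use. If use is centred at each visit's mean, b is the change at average use. A simulation used 600 samples of 40, outcome SD 6, within-person correlation 0.6, lognormal use with mean 480 minutes and CV 0.5 or 1.0, and a true day-90 change of −3 produced wholly by use (all assumed). The mean day-90 contrast was −2.99 and −2.97 with visit only, 0.11 and 0.05 with raw cumulative use added, and −2.99 and −2.97 with use centred at each visit. This tests a possible remedy; the SAP does not name cumulative use.

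**7. Precision.** The 95% half-width around a correlation of 0 is tanh(1.96/√(n − 3)). For n = 40: tanh(1.96/√37) = 0.31. For n = 32 (20% loss, assumed): tanh(1.96/√29) = 0.35.

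**The case against.** **The change models match the outcome definitions.** This stands. The protocol defines QOL and resilience as scores and changes over time, and the SAP analyses them so. The gap is between the models and the hypothesis and aim wording; the outcome definitions are not contradicted.

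**The meditation-time adjustment may cover all models.** The covariate sentence speaks of a single model and comes before the LASA and resilience sentence. Even if it were stretched, use would be an adjustment variable whose coefficient is not the stated target, and calm and active state would still be absent.

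**It is an exploratory feasibility study of 40 people.** This stands as a limit on severity. It does not supply an analysis for a stated hypothesis.

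**Stronger readings that the documents do not support.**
- A reader might infer that coping is not collected. The documents show only that no instrument is identified for it; one already in use may be intended.
- A reader might infer that the stress and sleep model is faulty because it holds both average and total use. The SAP does not define the average. It could be weekly time, 12-week time or session length, given that the primary outcome is described as "summarizing the frequency of use and duration of use each time it was accessed". The two terms could also be a legitimate between-person and within-person split. This is a request for definition.
- A reader might infer that hypothesis (a) needs a separate model. Step 6 of the working shows that centring use at each visit also serves.

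**Conclusion.** The point holds on the text, as a should-fix matter for the secondary aims. No use-response estimate is planned for LASA or resilience, neither Aim 2 exposure is modelled, and coping has no identified instrument. The undefined as-directed group and the undefined average are related but secondary.

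These counts rest only on the documents. The simulations rest on assumed inputs and show direction; they do not predict this trial's results. No figure is given for the overlap of average and total use, because it depends on a definition the SAP does not state. Nothing here bears on the primary adherence analysis.

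**What to change.** 1. **LASA and resilience.** Add a mixed-model analysis of post-baseline scores with baseline score, visit, age, sex and one prespecified use-time term, in the same metric as the stress and sleep model. Report its coefficient with a 95% CI. State which use applies at day 180, since use is planned to be assessed only to month 3. State how overnight wear counts: the protocol permits it and gives a battery life of about five hours, so if session duration records it, one night could add about 5 × 60 = 300 minutes.
2. **Hypothesis (a).** Report baseline-to-visit contrasts for stress and sleep, from a model without a use term or with use centred at each visit. Define the as-directed group once the protocol's use targets are reconciled.
3. **Stress and sleep model.** Define the average and how it differs from total time per interval. Keep one term, or both as an explicit between-person and within-person split.
4. **Aim 2.** If the session data supply them, model calm-state and active-state duration over a stated window for all four outcomes, with the same overnight rule. If calm share plus session time is used instead, say openly that it replaces the two durations. Otherwise amend Aim 2 to name use time as the exposure. The Server Data section lists EEG and per-session performance but not calm or active minutes, so supply must be confirmed.
5. **Coping.** State which collected instrument measures it, or delete it from the protocol's secondary outcomes, hypothesis (b) and the SAP analysis text.

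**Cost.** SAP wording, possibly a sentence or two of protocol text, and a few extra exploratory fits; no new visits, and no new questionnaires if coping is mapped to a collected instrument or deleted. Intervals will be wide. Use is chosen by participants and may itself be driven by stress or resilience, so both the use coefficients and the as-directed contrasts are associations. Brain-state data will be missing for guided sessions done without the headband.

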- **Satisfaction with the program:** This questionnaire is adapted from *Was it Worth it Questionnaire (WIWI)* to measure study and Muse-S™ satisfaction. It will be administered to the participants after completing the intervention at the end of the study, probing their satisfaction with the research study. These data could be used to assess the feasibility of the intervention by asking the patient if the entire research experience was worth it for them.

*Adherence to Intervention:*

- **Adherence to the Muse-S™** will be assessed by de-identified data available within the cloud, provided by InteraXon. InteraXon only has information per subject through subject ID only (as was provided by Mayo Clinic site), so when the cloud data is provided to Mayo, it will be linked to each subject through their study ID.

*Intervention:*

- **The Muse-S™ Headband system:** The Muse-S™ Headband system is a brain sensing headband that measures brain activity by detecting electrical impulses created by the brain. The Muse-S™ Headband system uses a series of focus attention training methods to train the brain. Each focus attention session can vary in length, with the ideal being a minimum of 10 minutes, and has been shown to reduce stress, anxiety, and improve focus and productivity. The Muse-S™ Headband system has seven sensors with four channels of EEG data for an accurate, high-quality experience. The battery life is approximately five hours and uses an industry-standard micro-USB charger. Twenty Muse-S™ Headband systems will be provided by the manufacturer at no cost in support of this study.

[figure not shown]
Use of Muse-S™ Headband systems will be demonstrated to each participant prior to their first mindfulness practice session, which will be completed during the baseline visit with the study coordinator. The study coordinator will present the participant with detailed instructions on how to begin each session. The frequency of the sessions thereafter will be at the participant’s discretion according to the study’s requirements (daily practice). Mindfulness training will follow the protocol in the Muse-S™ APP, which follows a standard breathing exercise with EEG brain state feedback through the mobile device, as designed by a panel of experienced mindfulness practitioners. In short, the Muse-S™ is a *FitBit* like device for the brain.

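### SAP secondary hypothesis (a) judges change from baseline only in as-directed users, a group formed by use after baseline, and the SAP states no change-from-baseline contrast for stress and sleep in all enrolled HCP

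*SAP*

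**What the plan says.** **Hypothesis.** SAP, Endpoints, Secondary Hypotheses (a), expects stress to fall and that "sleep score will be improved when compared to the baseline measures for those who use the Muse-S™ system as directed". The SAP does not define directed use.

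**Design.** Protocol, Methods: "All study participants will receive the Muse S™ Headband system at study entry". There is no control group, and the reference is each person's own baseline. Target accrual is 40.

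**Use.** Protocol, Methods, asks for use "at least 4 times per week for a minimum of 10 minutes each time over a period of 3 months (12 weeks") but adds: "If they are short on time, they can break up the 10 minutes and do shorter meditations". The Intervention text says "The frequency of the sessions thereafter will be at the participant’s discretion", qualified by the study's "requirements (daily practice"). Use is recorded from baseline to month 3, over the same period as the visits at days 14, 30 and 90.

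**Outcome as listed in the protocol.** The Aims section names "change in stress score over time" as a secondary outcome. Methods lists changes from baseline in QOL, stress, resilience and sleep. Neither is limited to adherent users.

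**Analysis.** The SAP's Data Analysis Plan gives stress and sleep a repeated-measures linear mixed model that estimates the association of average use with outcome level, adjusted for age, sex and meditation time per interval. Changes over time are specified for LASA, resilience, coping and cognitive testing, but not for stress and sleep. Results are point estimates with 95% CIs, and all analyses are labelled exploratory.

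**The concern.** Whether someone used the device as directed is known only after follow-up has begun. Workload could plausibly drive both perceived stress and the time available to practise. HCP whose load eases could then be over-represented among as-directed users and would look improved whatever the device did. Selection on high baseline stress would have a similar effect through regression to the mean. With no comparator, neither would be visible in the results.

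The analysis section does not rescue the hypothesis. An association between use and outcome level is not a change from baseline, and no such change is specified for everyone enrolled. An analyst asked to answer (a) as worded would have to form the subset. At stake is whether a statement that stress fell and sleep improved describes the HCP who were enrolled or only those who kept going.

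**Working it through.** The documents give no effect size, SD, alpha or power, so there is no planned figure to reproduce. The size of the problem can only be illustrated.

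**Inputs from the documents.** N = 40; single arm; 95% CI (nominal 2.5% in the favourable direction); PSS range 0 to 40, higher is worse.

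**Assumptions not in the documents.** No device effect and no time trend. Use and change in score are bivariate normal, with correlation r between use and improvement that the device did not cause. The as-directed share p is the top 30%, 50% or 70% of users.

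**Expected spurious improvement in the subset**, in SD units of change:

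r × φ(z₁₋ₚ) / p, where φ is the standard normal density.

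- p = 0.5: φ(0)/0.5 = 0.399/0.5 = 0.798. So r = 0.2 gives 0.16 and r = 0.4 gives 0.32.
- p = 0.3: φ(0.524)/0.3 = 0.348/0.3 = 1.159. So r = 0.2 gives 0.23 and r = 0.4 gives 0.46.

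**Simulation** (trials of 40, one-sample t interval on change within the subset). The means fall slightly below the formula because each trial has only 40 people.

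| As-directed share | Spurious fall, r = 0.2 to 0.4 | Favourable 95% CI |
|---|---|---|
| 30% (n = 12) | 0.23 to 0.45 SD | 11% to 34% |
| 50% (n = 20) | 0.16 to 0.31 SD | 10% to 29% |
| 70% (n = 28) | 0.10 to 0.19 SD | 7% to 18% |
| All 40 | 0 | 2.5% |

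At r = 0 every subset returns to 2.5%. With r of the opposite sign the subset shows a spurious worsening of the same size.

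**In PSS points.** Assume an SD of 6 and a baseline to follow-up correlation of 0.6. The SD of change is 6 × √(2 × (1 − 0.6)) = 5.37. With half adherent, 0.16 × 5.37 = 0.9 points and 0.31 × 5.37 = 1.7 points.

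**Selection on baseline stress instead.** With the same SD and correlation and half adherent, the expected fall is r × 6 × (1 − 0.6) × 0.798. For r = 0.3 to 0.5 this is 0.6 to 1.0 points, with a favourable CI in 7% to 12% of trials. If low-stress HCP adhere more (r = −0.3), the subset rises by 0.6 points and the rate drops to about 1%.

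**What an all-enrolled estimate does not remove.** With N = 40, SD 6 and correlation 0.6, a common fall of 1, 2 or 3 PSS points unrelated to the device gives a favourable CI in 21%, 63% or 93% of trials.

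**Directed use.** Four sessions a week for 12 weeks is 4 × 12 = 48 sessions, or 48 × 10 = 480 minutes. Daily practice is 7 × 12 = 84 sessions. The protocol's descriptions would therefore put different people in the subset, but any rule based on later use selects on behaviour after baseline.

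**The case against.** The strongest reply is that the SAP does not plan the analysis simulated above. A reader might infer from hypothesis (a) that a confidence interval in an as-directed subset is prescribed. It is not: the stated model uses average use and splits nobody. That stands, and it makes this a defect of the hypothesis and of its match to the model. It does not dispose of the point, because the model as written supplies no change from baseline in any group. A repeated-measures model may well carry visit terms, but the SAP names none as the stress or sleep estimate.

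A reader might also infer that the study's efficacy claim rests on this comparison. The documents do not support that. The primary outcome is adherence, (a) is secondary, no success rule depends on it, and all analyses are exploratory. This limits the consequence. But the label is given because of the number of outcomes, and it does not correct a biased estimate.

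Nor do the documents show that selection favours the device. Stressed HCP may use a stress tool more. The link between use and spontaneous change is assumed, and its sign is open.

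Finally, the protocol already lists the unrestricted outcome. That is true, and it is why the rewording brings the SAP into line with the protocol and adds nothing new to it.

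**Conclusion.** The point holds as a mismatch with a bias attached. Hypothesis (a) is framed in a self-selected group, the protocol's outcome is not, and the SAP states no estimate of change in stress or sleep for everyone enrolled. Answered as worded, (a) can show improvement with no device effect. With half of 40 as directed and r of 0.2 to 0.4, that is about 0.16 to 0.31 SD of change and a favourable CI in 10% to 29% of trials. These figures rest on the assumed correlation and share, normality, and no time trend.

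A reader might go further and conclude that false improvement is likely in this trial, or that analysing all enrolled would isolate the device effect. Neither follows. The bias vanishes or reverses under other correlations, and a single-arm pre-post change stays open to time trends and regression to the mean. The point merits a change to the SAP but does not touch the primary feasibility aim.

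**What to change.** 1. Reword secondary hypothesis (a) to refer to all enrolled HCP regardless of use, in line with the protocol's Aims and Methods.
2. In the Data Analysis Plan, add change-from-baseline contrasts at each visit for stress and sleep in all enrolled, and base the conclusion on those estimates and their 95% CIs. Take them from a fit without the use terms, since adjusting for use makes the change conditional on it again. The use-outcome association can stay as a separate analysis.
3. Report the as-directed subset beside these results, with its baseline values, as supplementary and self-selected. The descriptions of directed use in Methods and in the Intervention text must first be reconciled and one definition fixed in advance.
4. State that the all-enrolled estimate is itself an uncontrolled pre-post change that time trends or regression to the mean could produce.

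Cost: one reworded hypothesis, one added set of contrasts for two outcomes, and one sentence of interpretation. No new data are needed. If selection does favour adherent users, or if the device works and low users gain less, the headline estimate will be smaller than in the subset.
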